**Iopamidol
Protocol GM&RA
Synopsis**

CONFIDENTIAL

**A PROSPECTIVE, MULTICENTER OBSERVATIONAL STUDY TO
EVALUATE THYROID FUNCTION OF PEDIATRIC SUBJECTS
FROM BIRTH TO 3 YEARS EXPOSED TO
ISOVUE® (IOPAMIDOL INJECTION)**

IOPAMIDOL

Protocol No.: IOP-120

Final Protocol Date: 08 February 2017

[figure not shown]
IND No.: 16,272

Fully Amendment Synopsis: (including Amendment No.:01)

[figure not shown]
Final Version

15 June 2018

SPONSOR MEDICAL EXPERT:

Bracco Diagnostics Inc.

The information contained in this document is the property of Bracco Group. It contains strictly confidential information and no part of this document will be published or disclosed without Bracco Group prior written permission except that this document may be disclosed to appropriate Institutional Review Board/Ethics Committee/Regulatory Authorities/Competent Authorities as long as they are required to keep it confidential.

Protocol Title

A PROSPECTIVE, MULTICENTER OBSERVATIONAL STUDY TO EVALUATE THYROID FUNCTION OF PEDIATRIC SUBJECTS FROM BIRTH TO 3 YEARS EXPOSED TO ISOVUE® (IOPAMIDOL INJECTION)

Protocol No.

This study is being conducted under protocol number: IOP-120
IND number: 16,272

Objectives

Primary Objective(s)

- To evaluate the proportion of subjects, 0 to 3 years of age, with abnormal TSH values at either one month or two months after intravascular administration of ISOVUE.

Secondary Objective(s)

- To evaluate the proportion of subjects, 0 to 3 years of age, with hypothyroidism regardless of the need for thyroid hormone replacement therapy at either one month or two months after intravascular administration of ISOVUE.
- To estimate the proportion of subjects initiated on thyroid hormone replacement therapy

Investigational Plan

Overall Study Design Description

This is a Phase IV prospective, multicenter, observational study. Subjects 0 to 3 years of age who are required to undergo a radiologic procedure with intravascular administration of ISOVUE as part of their standard of care will be enrolled in the study. The specific iodine concentration and volume of ISOVUE used during the radiologic procedure will depend on the type of procedure and the standards in place at the site where the procedure is performed.

All subjects enrolled in the study will have thyroid function tests (TFT) which include serum TSH, total triiodothyronine (T3), total thyroxine (T4) and free T4 (fT4) assessed at baseline, at one month and two months following administration of ISOVUE. If TSH values are abnormal at either the one month or two month time points, further follow-up will be required at 6 and 12 months after the administration of ISOVUE to monitor subject's response and treatment (if any). Follow-up at 6 and 12 month post-dose time points will be performed using a pre-defined questionnaire.

The study will be conducted at approximately 10-20 sites in the United States.

Discussion of Study Design

The proposed study is designed as an intra-subject comparison of TSH, T3, and T4 values before and after administration of ISOVUE and will enroll pediatric subjects 0 to 3 years of age, who require a radiologic procedure with intravascular administration of ISOVUE as part of their standard of care.

The primary endpoint of this study is to evaluate the proportion of subjects exhibiting abnormal values of TSH following intravascular administration of ISOVUE. Thyroid function test data will be collected prospectively. Serum thyroid function testing at baseline, one month and two month post-dose time points will be performed at a local laboratory.

Abnormal TSH findings for subjects enrolled in the study will be compared to a reference population. As recommended by the FDA, the reference population for the study is represented by 3,214 infants who received potassium iodide prophylaxis on the second day of life at the time of the Chernobyl nuclear accident; 12 of the 3,214 infants ($p=0.003734$, 95% CI 0.002025, 0.006339) showed a transient increase of serum TSH levels and a decrease of fT4 levels after administration of potassium iodide.¹

As per FDA recommendation, sample size estimation for the current study has utilized the threshold incidence rate ($p=0.003734$) as the clinically meaningful value to rule out a safety concern about the proportion of children with abnormal TSH after exposure to ISOVUE.

Following FDA recommendations to be complied with:

- abnormal TSH in the study is defined as any TSH value above the normal age/gender-specific reference range provided by the respective local laboratories.
- hypothyroidism is defined as a TSH > 10 mIU/L (independent of fT4) or as a TSH above the normal age-specific reference range and an fT4 below the lower limit of the normal range.

Risk-Benefit Considerations

This study will enroll subjects who require a radiologic procedure with intravascular administration of ISOVUE as part of their standard of care; therefore, inclusion in the present clinical trial will not add any risk to the subject. Three blood draws of approximately 2.0 ml each will be performed in all subjects as part of the study, to assess serum TFTs before and after administration of ISOVUE.

Although subjects enrolled in the study will not directly benefit from this clinical trial, study results may be beneficial for pediatric subjects 0 to 3 years of age who will be exposed to iodinated contrast agents.

Study Duration

All subjects enrolled in the study will undergo the radiologic examination with administration of ISOVUE, as part of their standard of care; TFTs will be assessed at baseline, one month and two months post-dose.

If TSH values are abnormal at either the one month or two month time points, follow-up will be required at 6 and 12 months after the administration of ISOVUE to monitor subject's response and treatment (if any). Follow-up at the 6 and 12 month post-dose time points will be performed using a pre-defined questionnaire. Each follow-up will take no longer than 20 minutes.

Study Population

The study will be conducted in pediatric subjects 0 to 3 years of age, who are scheduled to undergo a radiologic procedure with intravascular administration of ISOVUE as part of their routine standard of care.

It is planned to enroll approximately 1,560 subjects in order to obtain 1,482 evaluable subjects.

Inclusion Criteria

Enroll a subject in this study if the subject meets the following inclusion criteria:

1. Is male or female from 0 to 3 years of age;
2. Is scheduled to undergo a radiologic examination that requires intravascular administration of ISOVUE as part of his/her standard of care;
3. Has normal baseline thyroid function tests (TSH, total T3, total T4, and fT4) performed at a local laboratory with blood sample obtained within one week prior to ISOVUE administration;
4. Written informed consent is obtained from the subject's parent(s) or legally acceptable representative(s) (according to local regulations) who are willing to comply with the protocol requirements.

Exclusion Criteria

Exclude a subject from this study if the subject does not fulfill the inclusion criteria, or if any of the following conditions are observed:

1. Has any known allergy to one or more of the ingredients of ISOVUE;
2. Has been diagnosed with congenital hypothyroidism;
3. Has undergone radiation treatments to the head or neck;
4. Is currently on thyroid replacement therapy;
5. Is on therapy with dopamine or any treatment which may affect the thyroid function testing results;
6. Has been exposed to any topical iodinated product within 30 days prior to enrollment in the present study;
7. Has been exposed to an iodinated contrast agent within 1 year prior to enrollment in the present study, including any administration of iodinated contrast agents during placement of a central line;
8. Has any medical condition or other circumstances which would significantly decrease the chances of obtaining reliable data, achieving study objectives, or completing the study and/or post-dose follow-up examinations.

Discontinuation Criteria

Clearly document the reason for the subject's discontinuation on the Case Report Form. Discontinued subjects are not replaced. Discontinue a subject from the study if the subject:

- Withdraws consent;
- No longer meets the Inclusion Criteria;
- Is lost to Follow Up

Investigational Products

The investigational product is ISOVUE® (Iopamidol Injection).

ISOVUE will not be provided to the participating sites since the study will enroll subjects undergoing a radiologic examination with intravascular administration of the contrast agent as part of their standard of care.

Methodology

Subject Evaluations

Demographic Information

Collect the following demographic information for subject's enrolled in the study:

- Date of Birth
- Gender
- Race
- Height (cm)
- Weight (kg)

Medical History

Obtain a complete medical history of subjects enrolled in the study, within 24 hours prior to the administration of ISOVUE. Report any clinical condition that might predispose to thyroid function abnormalities such as

- pre-term birth
- low or very low birth weight
- mother's exposure to iodinated contrast agents, iodine containing medications (e.g., Amiodarone, Potassium iodide), or topical iodinated product during pregnancy
- diagnosis of Down's Syndrome or other chromosomal abnormalities, congenital diseases, or Type I diabetes
- results of neonatal screening of thyroid function testing
- previous exposure to iodinated contrast agent (greater than 12 months prior enrollment in the present study).

Concomitant Medications

Record all medications (prescription and over-the-counter) taken within 24 hours prior to investigational product administration in the Concomitant Medication section of the Case Report Form. Additionally, record newly prescribed pharmacological treatments up to 1 week after administration of ISOVUE.

Safety Assessments

Monitor for any untoward medical occurrences that occur in the subject during the timeframe associated with the ISOVUE administration.

Laboratory Evaluations

A local laboratory will perform evaluation for the analytes listed in Table A.

A screening/baseline assessment of TFTs specified in Table A will be collected within 7 days prior to the administration of ISOVUE. Results must be obtained prior to enrollment into the study. Only subjects with normal TFT values will be enrolled into the study.

Blood samples for assessment of TFTs specified in Table A below will be collected at one month and two months post-dose.

Table A: Laboratory Analytes

Thyroid function test
TSH (Thyroid Stimulating Hormone)
fT4 (free Thyroxine)
Total T3 (total Triiodothyronine)
Total T4 (total Thyroxine)

Follow-up

If TSH is abnormal at either the one month or two month time points, the subject will undergo follow-up at 6 and 12 months after the administration of ISOVUE using a pre-defined questionnaire. Clinical data to be collected at 6 and 12 month follow-up will include, among the others:

- development of new symptoms which were considered to be related to the abnormal TFT values by the subject's physician;
- need for treatment related to the abnormal TFT values observed after the administration of ISOVUE; in case of treatment, the type of treatment, dosage, dose adjustments, start date and current status of treatment (i.e. ongoing, completed, stop date, etc.) will be collected and reported in the CRF;
- results of any additional TFT assessment performed in the interval time since the previous visit;
- results of thyroid ultrasound examinations, if any performed in the interval time since the previous visit;
- exposure to any iodinated contrast agent in the interval time since the previous visit;
- exposure to any topical iodinated product in the interval time since the previous visit.

A more detailed description of clinical data to be collected during follow-up will be provided in the questionnaire which will be a part of the CRF.

Imaging Procedures

Report the following information about the radiologic examination with intravascular administration of ISOVUE:

- type and indication of the radiologic examination (such as CT of the chest, urography, etc)
- date of examination
- contrast administration protocol, including route of administration (venous or arterial), iodine concentration (mgI/mL), and volume (mL) of ISOVUE administered.

Statistical Methods

In general, summary statistics (mean, median, standard deviation, minimum, and maximum) will be provided for continuous variables, and the number and percentage of each category will be provided for categorical data. Any changes in the original statistical methodology will be documented in the statistical analysis plan (SAP). All data collected will be presented in the listings.

All statistical analyses will be performed using SAS® software.

Subject Disposition and Demographic and Baseline Characteristics

Summary tables will be provided for the number of subjects who have been enrolled and completed according to the protocol. The number of subjects who prematurely discontinued the study and the reasons for their discontinuation will be summarized.

Summary statistics will be presented for demographic and baseline characteristics, including age, sex, race, height, weight, BMI, medical history, and other relevant study entry criteria.

Analysis Population

The safety population will consist of all enrolled subjects who had intravascular administration of ISOVUE. The analysis population will include subjects who received ISOVUE with TSH assessment at 1 month or two months post-dose. For subjects who received ISOVUE but do not have TSH assessment at 1 month or two months post-dose, the reasons for not having TSH assessment at 1 month or two months post-dose will be recorded and listed.

Concomitant Medications

Frequencies of concomitant medication use will be tabulated by World Health Organization (WHO) class, level I and level II.

Imaging Procedure

Data pertaining to the description of imaging procedure (type and indication of the radiologic examination) will be summarized.

Extent of Exposure

Descriptive statistics will be presented to summarize the concentration (mgI/ml) and volume (mL) of ISOVUE administered. The route of administration (venous or arterial) will also be summarized.

Primary Endpoint - Analysis for Abnormal TSH

The primary endpoint of this study is to evaluate the proportion of subjects, 0 to 3 years of age, with abnormal TSH values at either one month or two months after administration of ISOVUE. Following FDA recommendations, abnormal TSH in the study is defined as any TSH value above the normal age/gender-specific reference range provided by the respective local laboratories.

Abnormal TSH findings for subjects enrolled in the study will be compared to a reference population. As recommended by the FDA, the reference population for the study is represented by 3,214 infants who received potassium iodide prophylaxis on the second day of life at the time of the Chernobyl nuclear accident; 12 of the 3,214 infants ($p=0.003734$, 95% CI 0.002025, 0.006339) showed a transient increase of serum TSH levels and a decrease of fT4 levels after administration of potassium iodide.¹

The study hypothesis will be:

$$H_0: p \geq 0.003734$$

$$H_A: p < 0.003734$$

The proportion of subjects with abnormal TSH at either one month or two months after administration of ISOVUE and its 95% confidence interval will be estimated. Confidence interval will be calculated based on the approximate normal distribution:

$$95\% \text{ CI} = p \pm 1.96 * (p * (1-p) / n)^{1/2}$$

The number of subjects with shift in serum TSH (with respect to normal reference range) after exposure to ISOVUE will be cross tabulated and summarized separately. Each subject will serve as his/her own control, with the pre-dose values representing their baseline or control values.

Secondary Endpoint - Analysis for Hypothyroidism

The secondary endpoint is to evaluate the proportion of subjects, 0 to 3 years of age, with hypothyroidism regardless of the need for thyroid hormone therapy at either one month or two months after administration of ISOVUE.

Hypothyroidism is defined as a TSH $> 10 \text{ mIU/L}$ (independent of fT4) or as a TSH above the normal age/gender-specific reference range and a fT4 below the lower limit of the normal range.

The proportion of subjects with hypothyroidism at either one month or two months after administration of ISOVUE will be estimated and the 95% confidence interval will be presented.

For those subjects with hypothyroidism, follow-up data will be summarized by monitoring time points (6 months and 12 months).

Secondary Endpoint - Analysis for Thyroid Hormone Replacement Therapy

The proportion of subjects initiated on thyroid hormone replacement therapy will be estimated with 95% confidence interval.

Analysis for Other Safety Issues

Serious adverse events and non-serious adverse drug reactions will be summarized and listed.

Sample Size

The threshold incidence rate ($p=0.003734$) obtained from the Nauman and Wolff publication¹ will be used as the clinically meaningful value to rule out a safety concern about the proportion of children with abnormal TSH after exposure to ISOVUE. Using confidence interval method for the probability of observing a rare event, when no case is observed out of n , the upper 95% confidence limit of the incidence rate can be estimated by $3/n$. If no cases were observed in the sample size of 1,482, there is 95% confident to rule out an incidence rate of 0.002025 or higher. Considering a 5% drop out rate, 1,560 subjects will be enrolled in the study.

Interim Analyses

No interim analysis is planned.

References

¹ Nauman J, Wolff J. Iodide prophylaxis in Poland after the Chernobyl reactor accident: benefits and risks. Am J Med. 1993 May;94(5):524-32.

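### One post-dose TSH admits a child to the analysis, but a case is abnormal TSH at either of two visits: a small downward bias toward H_A

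*Protocol*

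**What the plan says.** Laboratory Evaluations plans two post-dose draws for every child: "Blood samples for assessment of TFTs specified in Table A below will be collected at one month and two months post-dose".

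Analysis Population requires only one of them: "The analysis population will include subjects who received ISOVUE with TSH assessment at 1 month or two months post-dose". For missing values that section offers a listing: "the reasons for not having TSH assessment at 1 month or two months post-dose will be recorded and listed".

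Primary Endpoint - Analysis for Abnormal TSH estimates "The proportion of subjects with abnormal TSH at either one month or two months after administration of ISOVUE". It gives one normal-approximation interval with a single n and tests H0: p ≥ 0.003734 against H_A: p < 0.003734.

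Study Population states: "It is planned to enroll approximately 1,560 subjects in order to obtain 1,482 evaluable subjects". Sample Size adds "If no cases were observed in the sample size of 1,482, there is 95% confident to rule out an incidence rate of 0.002025" or higher, and then "Considering a 5% drop out rate, 1,560 subjects will be enrolled in the study". Neither section says whether a child seen at only one visit is evaluable or belongs to the 5%.

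**The concern.** The endpoint needs two looks at each child, but the population rule accepts one. A child who is normal at the visit attended and absent from the other is in n with no abnormal value. No rule in the protocol gives that child any status other than non-case. If the missed visit would have been abnormal, a case is lost and the denominator stays the same. The reverse error cannot happen: a missed visit never creates a case.

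The study is meant to rule out a safety concern by showing a low proportion, so this error runs in the favourable direction. The counts are also very small: under the protocol's own interval, the conclusion turns on 2 versus 3 observed cases. Listing the reasons for missing TSH makes these children traceable but does not change the estimate. If the listing covers only children with neither value, one-visit children are not even listed.

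**Working it through.** **Inputs from the protocol.** Threshold 0.003734 and interval p ± 1.96·√(p(1−p)/n) (Primary Endpoint); the 3/n rule, 0.002025, n = 1,482, 5% drop-out and 1,560 enrolled (Sample Size).

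**Reproducing the plan's figures.** 3/0.002025 = 1,481.5, so 1,482. 1,482/0.95 = 1,560. Both hold.

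**Assumed, because the protocol gives neither.** f = share of analysed children with one visit; h = share of cases abnormal only at the missed visit. Missingness is taken as unrelated to the outcome. The value f = 5% borrows the size of the drop-out allowance for illustration; f = 20% is an extreme.

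**Bias.** Expected observed proportion = p·(1 − f·h).

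**Decision rule.** Upper limits under the protocol's formula:

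| n | 2 cases | 3 cases |
|---|---|---|
| 1,482 | 0.00322 | 0.00431 |
| 1,560 | 0.00306 | 0.00410 |

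At either n the threshold is excluded with at most 2 cases.

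**Effect at true p = 0.003734, n = 1,482.** Binomial probability of at most 2 cases at rate 0.003734·(1 − f·h):

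| f | h | 1 − f·h | Expected cases | P(≤ 2) |
|---|---|---|---|---|
| 0 | – | 1 | 5.53 | 0.086 |
| 5% | 0.10 | 0.995 | 5.51 | 0.088 |
| 5% | 0.25 | 0.9875 | 5.46 | 0.090 |
| 5% | 0.50 | 0.975 | 5.40 | 0.095 |
| 20% | 0.50 | 0.90 | 4.98 | 0.126 |

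If all 1,560 are analysed and 78 of them (5%) have one visit, the probability moves from 0.070 to 0.074 at h = 0.25.

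**One hidden case.** With three true cases, the chance that at least one is hidden is 1 − 0.9875³ = 0.037 (f = 5%, h = 0.25).

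**Separating this from the interval problem.** The 0.086 with complete data comes from the normal approximation. With an exact two-sided 95% limit at n = 1,560, at most 1 case excludes the threshold, and the probability goes from 0.020 to 0.021 (f = 5%, h = 0.25) or 0.033 (f = 20%, h = 0.50). At n = 1,482 only zero cases exclude it, and the probability goes from 0.0039 to 0.0042 (f = 5%, h = 0.25).

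**Zero-case statement.** This depends on where one-visit children sit.
- Within the 5% allowance (78 children analysed in addition to 1,482 with both values): 3/(1,482 + 78·0.75) = 0.00195 at h = 0.25, and at most 3/1,482 = 0.002024. The stated 0.002025 is kept.
- Among the 1,482 (5%, about 74): 3/(1,482 − 74·0.25) = 0.00205 at h = 0.25, and 3/1,408 = 0.00213 at h = 1. The stated figure is narrowly missed.

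Both stay well below 0.003734.

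**Size of the conservative alternative.** If the denominator is children with both values or any abnormal value, the estimate is multiplied by about (1 − f·h)/(1 − f). At f = 5% this is 0.9875/0.95 = 1.039 (h = 0.25) and 0.975/0.95 = 1.026 (h = 0.50). At f = 20% it is 0.95/0.80 = 1.19 and 0.90/0.80 = 1.125.

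**The case against.** **The non-case rule is inferred, not written.** This is true. One section says who is analysed and another says what a case is; neither names the child with one normal and one missing value. A reader might infer that the protocol expressly orders such children to be scored as normal, and it does not. The statistical methods section lets a SAP document changes, and that SAP is not shown. Even so, the population and the single-n proportion are fixed here, and applying them as written gives this result.

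**The population rule has merit.** It keeps a child who is abnormal at one visit and missing at the other. That stands, and the fix must preserve it.

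**The effect is small and its inputs are assumed.** This also stands. The 5% is a drop-out allowance, not a one-visit share, and nothing in the protocol supports f = 20%. A reader might infer that this defect causes the 0.086 false-exclusion probability. It does not: that figure arises with complete data from the interval method, and most of any gain from an exact interval belongs to that separate issue.

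**The sample size is not undermined.** A reader might infer that it is. The zero-case limit misses 0.002025 only if one-visit children are counted among the 1,482, and then by about 1% to 5%. The tested threshold is never approached.

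**Conclusion.** The point holds as a minor one. By the protocol's own population and endpoint rules, a missed visit can only lower the primary proportion among analysed children, and the direction favours H_A. The direction needs no assumption beyond reading those two rules together. The size rests on assumed f and h and on missingness unrelated to outcome: 0.5% to 2.5% low at f = 5%, and 10% low in the extreme setting. The chance of wrongly excluding the threshold rises by 0.002 to 0.009 at f = 5% (from 0.086 to 0.088–0.095), and by 0.040 in the extreme setting (to 0.126).

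The documents do not support a claim that the primary conclusion is unreliable for this reason alone. Children with no post-dose TSH at all are a different question and are not covered here.

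**What to change.** 1. Keep every child with any abnormal post-dose TSH as a case. Do not treat one normal plus one missing value as a fully observed non-case.
2. Estimate the either-visit risk by a likelihood that uses all observed visits, including children seen only at month 2. At the least, add a pre-specified conservative analysis whose denominator is children with both values or any abnormal value, and require the conclusion against 0.003734 to hold there as well. That denominator errs upward, by about 3–4% at f = 5% and 12–19% at f = 20% (h = 0.25 to 0.50), so it should not be presented as unbiased.
3. Define the 1,482 evaluable as children with both values or any abnormal value, state that the 5% allowance covers one-visit children, and report their number by visit missed.

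Do not use 1 − (1 − p1)(1 − p2), where p1 is the month-1 proportion and p2 is restricted to children normal at month 1. It drops a case seen only at month 2. For example, take 1,482 children with 37 missing each visit and three cases, two found at month 1 and one seen only at month 2. It gives 2/1,445 = 0.00138 against 3/1,482 = 0.00202, and an implied effective n of 3/(2/1,445), about 2,167, which exceeds the number analysed.

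Cost: wording and one table, with no new data. The estimate and upper limit become slightly less favourable, and the likelihood assumes that missed visits are unrelated to the unseen result. The gain is also limited: under the protocol's normal-approximation interval, 2 cases over 1,408 children still give an upper limit of 0.00339, so at f = 5% the conservative analysis would not move the 2-case cut-off.

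### The normal-approximation interval fixed for the primary proportion collapses to [0, 0] with no cases, the outcome used to size the study, and clears the 0.003734 threshold with 2 cases when exact limits do not

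*Protocol*

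**What the plan says.** The protocol section Primary Endpoint - Analysis for Abnormal TSH tests H0: p ≥ 0.003734 against HA: p < 0.003734. It then fixes how the primary proportion is to be reported: "Confidence interval will be calculated based on the approximate normal distribution", followed by the formula p ± 1.96·(p(1−p)/n)^(1/2). It gives no exact method, no provision for zero events and no other test. It does not say in words when H0 is rejected.

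The Sample Size section says that the threshold "will be used as the clinically meaningful value to rule out a safety concern about the proportion of children with abnormal TSH". It bases the number of subjects on a different interval. When no case is seen, "the upper 95% confidence limit of the incidence rate can be estimated by" 3/n, and the calculation is anchored to one outcome: "If no cases were observed in the sample size of 1,482", a rate of 0.002025 or higher is ruled out. With 5% drop-out this gives 1,560 enrolled.

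The Statistical Methods section leaves room for later changes: "Any changes in the original statistical methodology will be documented in the statistical analysis plan (SAP)".

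**The concern.** The study is meant to exclude a rate of 0.003734, so the upper confidence limit carries the conclusion. The Wald interval estimates its standard error from the observed proportion. When very few cases are seen, that standard error is too small, and with none it is zero. Those are the only results with which this study could succeed.

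Two consequences follow. First, the analysis section and the sample size section give incompatible upper limits for the same result, 0 of 1,482. Second, the interval may exclude the threshold when the data do not support it. In a safety study in children aged 0 to 3 years, that error runs towards a false reassurance.

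**Working it through.** **Inputs.** n = 1,482 evaluable, 5% drop-out and the 3/n rule (Sample Size). Threshold p0 = 0.003734 and the Wald formula (Primary Endpoint - Analysis for Abnormal TSH).

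**The plan's own figures.** 3/0.002025 = 1,481.5, rounded up to 1,482; conversely 3/1,482 = 0.002024. 1,482/0.95 = 1,560. The sample size arithmetic reproduces.

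**Cases expected at the threshold.** 1,482 × 0.003734 = 5.53.

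**Upper limits by number of cases x.** Wald: x/n + 1.96·√[(x/n)(1−x/n)/n]. Exact (Clopper-Pearson): the 0.95 quantile (one-sided) or 0.975 quantile (two-sided) of Beta(x+1, n−x). The last column is the binomial probability P(X ≤ x) at p0.

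| x | Wald upper | Exact one-sided 95% | Exact two-sided 95% | P(X ≤ x) at p0 |
|---|---|---|---|---|
| 0 | 0 | 0.002019 | 0.002486 | 0.0039 |
| 1 | 0.001997 | 0.003197 | 0.003754 | 0.0256 |
| 2 | 0.003219 | 0.004242 | 0.004866 | 0.0859 |
| 3 | 0.004313 | 0.005224 | 0.005904 | 0.1974 |

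**Zero cases.** The standard error is √(0 × 1/1,482) = 0, so the interval is [0, 0]. The sample size section gives 0.002024 for this result, which agrees with the exact one-sided limit of 0.002019. So 3/n is a one-sided 95% limit, and the printed formula cannot reproduce it.

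**Two cases.** p = 2/1,482 = 0.001350 and SE = √(0.001350 × 0.998650/1,482) = 0.000954. The upper limit is 0.001350 + 1.96 × 0.000954 = 0.00322, below 0.003734. The lower limit is −0.00052, an impossible value. Both exact upper limits lie above the threshold.

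**Type I error.** Assume H0 is rejected when the upper limit is below 0.003734.
- Wald: rejects for X ≤ 2, error 0.086. A multiplier of 1.645 gives the same cut-off, since 3 cases yield 0.002024 + 1.645 × 0.001168 = 0.00394, still above the threshold.
- Exact one-sided 95%: rejects for X ≤ 1, error 0.0256.
- Exact two-sided 95%: rejects for X = 0 only, error 0.0039.

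**Is this only the conservatism of the exact method?** No. With 2 cases the Wilson score upper limit is 0.00407 (one-sided) or 0.00491 (two-sided), both above the threshold.

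**Coverage.** Summing binomial probabilities over the counts whose Wald interval contains the true rate, the nominal 95% interval covers 52% of the time at a true rate of 0.0005, 77% at 0.001 and 79% at 0.002.

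**The reference rate.** For 12/3,214 the Wald formula gives (0.00163, 0.00584). The protocol prints (0.002025, 0.006339), so it does not use Wald limits for the rate with which the study is compared.

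**The case against.** The strongest objection is that the protocol never states that H0 is rejected when the Wald upper limit falls below 0.003734. It states the hypotheses and, separately, that an interval will be estimated. The test may sit in a SAP that is not at hand. This stands as a limit on the 8.6% figure, which is conditional on the assumed rule. It does not touch the zero-case conflict or the poor coverage, which need no rule. The assumed rule is also the natural one, because no other test is named and the sample size section argues from a confidence limit.

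Second, the zero-case defect changes no decision: 0, 0.00202 and 0.00249 are all below 0.003734. That is true, but the reported interval would still claim no uncertainty at all.

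Third, measured against the one-sided exact limit, the methods disagree only at exactly 2 cases. The probability of that count is 0.060 at the threshold and 0.016 at a true rate of 0.005. If 1% of children had abnormal TSH (an assumption; no expected rate is given), about 15 cases would arise and every method would fail to reject. This also stands: the discrepancy matters only if the true rate is near or below the threshold. That is the situation in which the study could succeed.

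Fourth, the multiplier 1.96 makes the printed interval two-sided, so adopting a one-sided 95% limit would change the standard as well as the method. This is fair. The two sections imply different standards, and the correction has to choose one openly.

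**Conclusion.** The concern holds. The protocol states a specific formula that is unsuitable for the counts on which this study turns, and the SAP's absence does not excuse it. Under any decision rule, the analysis cannot yield the zero-case upper limit that justifies the 1,482 subjects. With 2 cases the Wald limit of 0.00322 excludes 0.003734, while exact limits of 0.00424 and 0.00487 do not. On the assumption that H0 is rejected when the upper limit is below the threshold, the type I error is 8.6%, against 5% on the one-sided standard implied by 3/n or 2.5% if the two-sided 95% interval governs.

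No discrepancy is claimed for 1 case at n = 1,482, where the exact answer depends on sidedness (0.00320 against 0.003754). The sample size arithmetic itself is sound. The formula must be corrected before the primary analysis.

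**What to change.** Replace the Wald formula for the primary proportion with the Clopper-Pearson exact interval, and add the decision rule: H0 is rejected if the exact one-sided 95% upper limit is below 0.003734. This matches the standard implied by 3/n and tolerates 0 or 1 case at 1,482 evaluable subjects. If a two-sided 95% limit is intended, say so, and state that only 0 cases is then tolerated. A Wilson interval would also remove both defects, but the exact interval is the one consistent with the 3/n argument.

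The change is one formula and one sentence, documented in the SAP as the protocol allows. No data collection changes. In SAS, PROC FREQ with exact binomial limits does it, and alpha = 0.10 gives the one-sided 95% upper limit.

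The real cost is a lower probability of rejecting H0:

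| True rate | Wald (X ≤ 2) | Exact one-sided (X ≤ 1) | Exact two-sided (X = 0) |
|---|---|---|---|
| 0.001 | 81% | 56% | 23% |
| 0.0005 | 96% | 83% | 48% |

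To keep tolerating 2 cases under the exact one-sided 5% rule, the smallest n with P(X ≤ 2) ≤ 0.05 at p0 is 1,684 evaluable, or 1,684/0.95 = 1,773 enrolled, instead of 1,482 and 1,560.
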